3.4. Endpoints/Outcomes Measurements

3.4.1. Primary outcomes.

The primary short term study endpoints will be the time required for hemostasis, and the time required from the end of the ablation procedure until the patient leaves the EP Lab.

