All patients undergoing ablation for atrial fibrillation with the Cryo Balloon will be eligible to participate. Any patient who is under age 18 years of age, pregnant, or with an untreated DVT(s) will be excluded from participation.

Study Methodology: Summarize study treatment/interventions as well as if there is a control group/randomization. Identify primary and secondary outcomes.

The primary short term study endpoints will be the time required to obtain hemostasis, and for the time required from the completion of the ablation portion of the procedure until the patient leaves

the EP Lab. Secondary end points include groin complications including bleeds, additional pressure required for hemostasis, hematoma, pseudoaneurysm, and transfusion.

Statistical Methodology: Continuous variables will be expressed as the mean +/- SD. Univariate comparisons will be performed on continuous variables with either paired T test, unpaired T test or analysis of variance, as appropriate. Categorical variables will be compared with Chi-square analysis. Statistical significance will be considered present with a p value ≤ 0.05 .

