1.2. Hypothesis

The hypothesis of this study is that the Figure of 8 Technique to obtain hemostasis after Cryoballoon ablation for AF will take less time, and be associated with a lower frequency of groin complications.

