4. STATISTICAL CONSIDERATIONS/DATA ANALYSIS

4.1. Sample Size

Provide justification of the sampling procedure and sample size. Delineate methods used to estimate the required number of subjects.

The estimated time +/- SD for the control and study groups is estimated at 30 +/- 15mins and 15 +/- 5 mins, respectively. Using a power calculation to identify an 90% power, then 10 patients in each group will be required. If however, the study group mean is 20 mins, and the sd is 16 mins, then 33 patients per group would be required. Therefore, to account for drop out, and/or a mistake in any of the above assumptions, the plan is to aim for 50 patients in each group.

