4.2. Method of Data Analysis

Data collection will occur just prior to, and during the ablation procedure. Also, data will be collected at before hospital discharge after the procedure (usually the next day), and at the 1 month outpatient follow up visit. Data entry will be directly the statistical program, SAS. Continuous variables will be expressed as the mean +/- SD. Univariate comparisons will be performed on continuous variables with either paired or unpaired T test, or analysis of variance, as appropriate. Categorical variables will be compared with Chi-square analysis. Statistical significance will be considered present with a p value ≤ 0.05 . Please see section 4.1 above for the power calculation.

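### Two primary time endpoints have no success rule or test order; if either alone may carry the claim, the false positive rate exceeds 5% (up to 9.75%)

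*Combined protocol and SAP*

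**What the plan says.** - **Endpoints.** Section 3.4.1 reads: "The primary short term study endpoints will be the time required for hemostasis, and the time required from the end of the ablation procedure"; the second interval ends at exit from the EP Lab. The abstract (Study Methodology) gives the same pair: "the time required to obtain hemostasis, and for the time required from the completion of the ablation portion of the procedure", again ending at lab exit. Neither place ranks them.
- **Tests.** The abstract (Statistical Methodology) says: "Univariate comparisons will be performed on continuous variables with either paired T test, unpaired T test or analysis of variance", as appropriate. Section 4.2 has nearly the same sentence and then one general threshold: "Statistical significance will be considered present with a p value" of 0.05 or less. Neither place states whether tests are one- or two-sided, and neither mentions multiplicity.
- **Sample size.** Section 4.1 begins "The estimated time +/- SD for the control and study groups is estimated at" 30 ± 15 and 15 ± 5 minutes, without saying which of the two times is meant.
- **Hypothesis.** Section 1.2 states that "the Figure of 8 Technique to obtain hemostasis after Cryoballoon ablation for AF will take less time", again without saying which time decides.

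Section 2.2 is not in the text available. Its position between study type and duration makes it an unlikely place for a testing rule.

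**The concern.** Two primary endpoints need a rule that turns two p values into one conclusion. Without it, two things go wrong.

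First, a split result has no agreed reading. Such a result is plausible because the two times need not move together. As the abstract and 1.1 describe it, the manual arm has an ACT check, protamine and a repeat ACT before the sheaths are pulled. The plan does not say when the hemostasis clock starts. If it starts at sheath removal, that waiting counts towards lab-exit time but not towards hemostasis time. One comparison could then be significant and the other not.

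Second, nothing prevents a claim based on whichever endpoint reached p ≤ 0.05. The trial is not blinded (2.1, 3.6), so a rule fixed in advance is a useful protection against choosing the emphasis after the results are known.

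**Working it through.** **1. The plan's own figures (4.1).** With n per group = (SD₁² + SD₂²)(z_α + z_β)² / difference² and 90% power (z_β = 1.282):

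- Base case, 30 ± 15 vs 15 ± 5, two-sided 0.05: (225 + 25)(1.960 + 1.282)² / 225 = 11.7, so 12.
- The same, one-sided 0.05: (225 + 25)(1.645 + 1.282)² / 225 = 9.5, so 10.

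Section 4.1 states "Using a power calculation to identify an 90% power, then 10 patients in each group will be required". That equals the one-sided result and is two below the two-sided one, so sidedness cannot be taken for granted. The 33 per group for the less favourable case does not reproduce at 90% power (51 two-sided, 42 one-sided). That is a separate matter and does not affect this point. Only one endpoint enters either calculation.

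**2. Overall false positive rate if either endpoint suffices.** Inputs: two endpoints (3.4.1) and 0.05 for each (4.2). Assumptions: neither time truly differs, and the two test statistics are bivariate normal with correlation ρ. The documents give no ρ, so a range is shown.

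Two-sided: error = 1 − P(|Z₁| ≤ 1.960 and |Z₂| ≤ 1.960). At ρ = 0 this is 1 − 0.95² = 0.0975.

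| ρ | Two-sided | One-sided |
|---|---|---|
| 0 | 9.75% | 9.75% |
| 0.5 | 9.1% | 8.8% |
| 0.8 | 7.8% | 7.5% |
| 0.9 | 7.0% | 6.8% |
| 0.95 | 6.5% | 6.3% |
| 0.99 | 5.7% | 5.6% |
| 1 | 5.0% | 5.0% |

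Under any dependence the bound is 0.05 + 0.05 = 10%.

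**3. Under other rules.** If both endpoints must be significant, an overall false positive requires each test to be significant, so the error is at most 5%. In a fixed sequence the second test is reached only after the first succeeds, so with neither time differing the error is again at most 5% at any ρ.

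**4. Power for the first-tested endpoint.** Two-sample t-test, two-sided. The less favourable case in 4.1 is introduced by "If however, the study group mean is 20 mins, and the sd is 16 mins"; the control group is assumed to stay at 30 ± 15. The noncentrality is 10 / √((225 + 256)/n), which is 3.22 at n = 50.

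| n per group | α = 0.05 (fixed sequence) | α = 0.025 (even split) |
|---|---|---|
| 50 | 89.1% | 82.7% |
| 45 (illustrative, after dropout) | 85.7% | 78.0% |

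In the base case power exceeds 99.9% in all four cells.

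**The case against.** The strongest reply is that 9.75% is the extreme. It requires that either endpoint suffices and that the two times are uncorrelated, and the plan states neither. The endpoints are joined by a conjunction that could mean both are required, in which case there is no inflation. Under the abstract's wording the lab-exit interval contains hemostasis, so a positive correlation is expected. Section 4.1 also anticipates a difference of 10 to 15 minutes, whereas the inflation concerns the case of no difference. Finally, a both-required rule or Holm's procedure would control the error as well as a fixed sequence does.

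Much of this stands as a matter of emphasis. The 9.75% is a ceiling, and the realistic figure is probably lower. A fixed sequence is one of several sound choices.

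The gap itself remains. A conjunction in a list of endpoints is not a success criterion, and being listed first does not make hemostasis time the lead endpoint. Correlation below 1 reduces the excess without removing it, and it does not say how to read a split result. Nor does an expected large effect make error control unnecessary: 1.3 says it is unknown which technique takes less time, and 4.1 itself allows for mistaken assumptions.

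**Conclusion.** The concern holds. The main defect is the missing decision rule, which leaves a discordant result uninterpretable whatever the true effect. The error inflation is conditional on either endpoint being enough for a claim and on neither time truly differing. Under those conditions the rate is above 5% at any correlation below 1 and reaches 9.75% at most for normal test statistics. One-sided testing gives similar figures. This should be corrected, and the correction is cheap; it does not invalidate the design.

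**What to change.** In the abstract, 3.4.1 and 4.2, state that tests are two-sided and follow a fixed sequence: time to hemostasis first at 0.05, then lab-exit time at 0.05 only if the first is significant. In 4.1, say which endpoint the planning time refers to. If it is lab-exit time, reverse the order so that the powered endpoint is tested first.

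The start of the lab-exit interval should also be worded identically in the abstract and 3.4.1. One runs from completion of the ablation portion and the other from the end of the ablation procedure, and this affects how far the two times overlap.

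The cost is a few sentences, with no extra patients or data. The first endpoint keeps its full power, unlike under an even split of alpha. The price is that lab-exit time cannot be claimed if the first test fails. If the investigators find that unacceptable, Holm's procedure removes the dependence on order; if they intend both times to be required, saying so also holds the error at 5%. Whichever rule is chosen should be written down before the outcome data are examined.

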3.4.2. Secondary outcomes

Secondary end points include groin complications including bleeding, hematoma, pseudoaneurysm, and transfusion.

3.5. Consent/Assent

Written informed consent with an IRB approved consent form will be utilized. Consent will be obtained by the PI, SI, or IHVI research staff with training to obtain the consent. Consent will generally be obtained in the office, or prior to the procedure in IFH. Research personnel are likely to contact prospective participants by phone, when the PI/SI asks them to do so.

3.6. Monitoring Subjects and Criteria for Withdrawal of Subjects from the Study.

Beyond what is required for a standard cryoballon ablation for atrial fibrillation, there will be no additional tests, admissions, or outpatient visits. Participants will be seen the day after the ablation and one month later by an investigator, as is currently done. The study is not blinded, and a monitor will not be used. Participants can withdraw from study participation at any time. The study will stop when 100 patients have been randomized, and follow up completed.

4. STATISTICAL CONSIDERATIONS/DATA ANALYSIS

4.1. Sample Size

Provide justification of the sampling procedure and sample size. Delineate methods used to estimate the required number of subjects.

The estimated time +/- SD for the control and study groups is estimated at 30 +/- 15mins and 15 +/- 5 mins, respectively. Using a power calculation to identify an 90% power, then 10 patients in each group will be required. If however, the study group mean is 20 mins, and the sd is 16 mins, then 33 patients per group would be required. Therefore, to account for drop out, and/or a mistake in any of the above assumptions, the plan is to aim for 50 patients in each group.

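### The fallback of 33 patients per group in section 4.1 does not follow from its own inputs: 90% power needs 51–52 (two-sided) or 42 (one-sided)

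*Combined protocol and SAP*

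**What the plan says.** Section 4.1 (Sample Size) starts from a base case: "The estimated time +/- SD for the control and study groups is estimated at 30 +/- 15mins and 15 +/- 5 mins, respectively". It continues: "Using a power calculation to identify an 90% power, then 10 patients in each group will be required". It then gives the fallback: "If however, the study group mean is 20 mins, and the sd is 16 mins, then 33 patients per group would be required". From these two figures it reaches the planned size: "Therefore, to account for drop out, and/or a mistake in any of the above assumptions, the plan is to aim for 50 patients" per group.

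The significance level is in section 4.2 (Method of Data Analysis), not in 4.1: "Statistical significance will be considered present with a p value ≤ 0.05". Section 4.2 also points back: "Please see section 4.1 above for the power calculation". Allocation is 1:1 (section 3.2). Sidedness is stated nowhere. The hypothesis in section 1.2 is directional, namely that the suture technique "will take less time, and be associated with a lower frequency of groin complications", but no one-sided test is declared. No drop-out rate is given.

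**The concern.** The fallback cuts the difference from 15 to 10 min and raises the study-group SD from 5 to 16 min. The required number is proportional to the sum of the two variances divided by the squared difference. That ratio rises from (225 + 25)/225 = 1.11 to (225 + 256)/100 = 4.81, a factor of 4.33. Starting from 10 per group, one would expect a figure in the low forties, and 33 is well below that.

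The figure matters because 33 is the number that 50 is meant to exceed. A reader takes 50 as the fallback requirement plus 50 − 33 = 17 patients per group, held against drop-out and mistaken assumptions. If 33 is too low, that reserve is smaller than it appears or does not exist.

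**Working it through.** **Inputs.** Control 30 ± 15 min, fallback study group 20 ± 16 min, and 90% power (section 4.1); alpha 0.05 (section 4.2); 1:1 allocation (section 3.2); unpaired comparison of two means (section 4.2 lists the unpaired t test among its options). Two points are assumed: the fallback sentence repeats neither the power nor the control SD, so 90% and 15 min are carried over. Both sidedness options are computed.

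**Formula.** n per group = (z_alpha + z_beta)² × (SD1² + SD2²) / difference². At 90% power the first factor is (1.960 + 1.282)² = 10.507 two-sided and (1.645 + 1.282)² = 8.564 one-sided. The t figures use the noncentral t distribution.

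**Base case (the plan says 10).** Difference 15, SDs 15 and 5:
- one-sided: 8.564 × 250/225 = 9.52, so 10 (t: 11)
- two-sided: 10.507 × 250/225 = 11.67, so 12 (pooled t: 13; Welch: 14)

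The plan's 10 is reproduced exactly by the one-sided normal formula.

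**Fallback (the plan says 33).** Difference 10, SDs 15 and 16:
- two-sided: 10.507 × 481/100 = 50.5, so 51 (t and Welch: 52)
- one-sided: 8.564 × 481/100 = 41.2, so 42 (t and Welch: 42)

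**Other readings of the SD, still at 90% power and alpha 0.05** (ranges run from the normal to the t or Welch figure):

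| SDs (control/study) | Two-sided | One-sided |
|---|---|---|
| 16/16 | 54–55 | 44–45 |
| 15/15 | 48–49 | 39–40 |
| 16/5 | 30–32 | 25–26 |

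None gives 33. The nearest, 16/5, moves the 16 to the control group. That conflicts with the sentence, which attaches it to the study group mean, and with the printed control SD of 15.

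**Ways to reach 33 by changing a stated input.** At 80% power with SDs of 15 and 16, the results are 38–39 two-sided and 30–31 one-sided. Some combinations do land on 33, for example:
- 80% power, one-sided, common SD 16: 31.7, so 32 (t: 33)
- 85% power, one-sided, common SD 15: 32.35, so 33 (normal)
- 95% power, two-sided, SDs 15 and 5: 32.49, so 33 (normal)

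Each abandons the stated 90%, and the text documents none of them.

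**Power with SDs of 15 and 16, difference 10 (normal / t):**

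| n per group | Two-sided | One-sided |
|---|---|---|
| 33 | 0.745 / 0.732 | 0.835 / 0.828 |
| 45 (assumed 10% loss) | 0.864 / 0.857 | 0.921 / 0.918 |
| 50 | 0.897 / 0.891 | 0.943 / 0.940 |

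Simulation of the t test with 200,000 trials agrees: at n = 33, 0.733 two-sided and 0.829 one-sided; at n = 50, 0.891 and 0.941. With 33 per group, 90% power would need a true difference of 12.6 min two-sided or 11.3 min one-sided, not 10.

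**Reserve at 50 per group.** As printed: 50 − 33 = 17. Two-sided: 50 − 52 = −2. One-sided: 50 − 42 = 8.

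**The case against.** The strongest reply is that the plan's own base case points to a one-sided calculation. At 90% power, 10 per group matches the one-sided normal formula and falls short two-sided, and the hypothesis is directional. If one convention served both scenarios, the fallback is 42, and 50 per group leaves 8 spare with 94% power. The claim that no reserve exists therefore depends on a two-sided test, which the plan does not state either. This stands, and it is why both figures are given. It does not rescue 33, which is 9 per group short even one-sided. Nor does it settle the convention, since an unqualified 0.05 threshold would commonly be read as two-sided.

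A second reply is that the effect is small. Fifty per group gives 89–94% power in the fallback and over 99.9% in the base case, and the worst shortfall is 2 patients per group. That also stands, and it limits the point to the written justification.

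Third, the 90% power and the control SD are carried into the fallback sentence by assumption, and the split into 33 plus 17 spare is an inference from the word order of section 4.1. Both are fair cautions. However, no other power or control SD is given, and the section presents 50 as a margin over the figures just stated.

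**Conclusion.** The concern holds. On the printed inputs, with 90% power and a control SD of 15 min carried over and alpha at 0.05, the fallback needs 51–52 per group two-sided or 42 one-sided. The stated 33 is too low by 18–19 or by 9, which is more than rounding or choice of formula can explain. Power at 33 per group is about 73% or 83% (t).

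The reserve implied by section 4.1 shrinks from 17 per group to 8 (one-sided) or disappears (two-sided). If the test is two-sided, any loss takes power further below target: about 86% with an assumed 45 evaluable per group.

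The documents do not show whether the 33, the 16, or an unreported change of power, sidedness or SD is the cause. The base-case 10 is not challenged, and neither are the planned total of 100 patients and the conduct of the trial.

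**What to change.** Keep 100 patients. Recover the calculation behind 33 and find which input differs from the text. Then revise section 4.1 to:

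- state alpha, sidedness, power and both SDs for each scenario;
- replace 33 with the figure that follows. With SDs of 15 and 16 at 90% power this is 52 per group two-sided, with a note that 50 gives about 89%, or 42 one-sided, with a note that 50 gives about 94%;
- keep the wording about a margin for drop-out above the fallback only if the corrected figure supports it.

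The cost is a wording correction and, if the test is two-sided, a less favourable statement: about 89% power under the fallback and no reserve. No patients are added and nothing in the conduct changes.

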4.2. Method of Data Analysis

Data collection will occur just prior to, and during the ablation procedure. Also, data will be collected at before hospital discharge after the procedure (usually the next day), and at the 1 month outpatient follow up visit. Data entry will be directly the statistical program, SAS. Continuous variables will be expressed as the mean +/- SD. Univariate comparisons will be performed on continuous variables with either paired or unpaired T test, or analysis of variance, as appropriate. Categorical variables will be compared with Chi-square analysis. Statistical significance will be considered present with a p value ≤ 0.05 . Please see section 4.1 above for the power calculation.

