**Randomized Trial of Femoral Vein Hemostasis After Ablation for Atrial Fibrillation with
manual pressure versus a Figure of 8 suture.**

Principal Investigator
S. [name]

Sub-Investigator(s)
[name], MD
[name], MD
[name], MD
[name], MD
[name], MD
[name], MD
[name], MD
[name], MD
[name], MD

Sponsor
NA

Site of Investigation
IFH

Date of Protocol
02 November 2016

ABSTRACT

Title: Randomized Trial of Femoral Vein Hemostasis After Ablation for Atrial Fibrillation with manual pressure versus a Figure of 8 suture.

Short Title: Femoral Vein Hemostasis.

Rationale: Patients who undergo ablation for atrial fibrillation typically have 2 sheaths placed in each groin, including a large sheath when the Cryo Balloon is used for pulmonary vein isolation. During the procedure, heparin is administered to maintain a target ACT > 300 seconds. At the conclusion of the procedure, the venous sheaths are removed and hemostasis is obtained. There are at least 2 ways of obtaining hemostasis after venous access. In the manual hemostasis approach, an ACT is checked and protamine is administered. The ACT is rechecked 20" later, and if < 220 msec, the sheaths are pulled and hemostasis is achieved with manual pressure (Manual Hemostasis Group). Another conventional approach is to place a Figure of 8 suture around the sheaths in each groin to achieve hemostasis as the sheaths are removed, and therefore obviate the need for assessment of the ACT, protamine administration, and manual pressure (Figure of 8 Group).

Objectives: The goal of this study is to compare the safety and efficacy of obtaining hemostasis after an ablation for atrial fibrillation with the Manual Hemostasis Technique versus with the Figure of 8 Technique.

Study Type: This is a non-blinded, prospective, randomized trial.

Study Design: Number and types of subjects to be enrolled, study location, study duration, inclusion/exclusion criteria.

100 (50 in each group) patients undergoing Cryo balloon ablation for ablation of atrial fibrillation will be randomized to the Manual Hemostasis Group or to the Figure of 8 Group for venous hemostasis. Clinical characteristics, medications, procedure duration, heparin dosage, and post procedure anticoagulation will be collected. Follow up will end when the patient is seen in the office one month after the ablation procedure.

The study location will be the EP Laboratories at IFH, and the EP MDs outpatient offices.

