3.2. Control Group

Is there a control group? The control group may be receiving no treatment or a standard treatment. Will randomization be required?

Patients will be randomized 1:1 to either the Manual Hemostasis Group (Control) or to the Figure of 8 Hemostasis Group.

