3.3. Randomization

Patients will be numbered as they are randomized into the study. For instance, the first patient randomized, will be patient 001, and so on. The IHVI Research Center will serve as the randomization center. When the procedure is to begin, the randomization will be

provided. Randomization will be performed by a random number generator. Patients who receive an odd number, will be randomized to the control group, i.e., manual hemostasis.

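### Both primary times are to be compared only by unadjusted tests although baseline data are collected: a valid analysis that may give up some precision

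*Combined protocol and SAP*

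**What the plan says.** Section 3.4.1 names two continuous times as primary: "The primary short term study endpoints will be the time required for hemostasis, and the time required from the end of the ablation procedure" to departure from the EP laboratory. For continuous variables section 4.2 states: "Univariate comparisons will be performed on continuous variables with either paired or unpaired T test, or analysis of variance, as appropriate". The abstract's statistical paragraph says the same in substance. The available text contains no regression model, covariate list or adjusted sensitivity analysis.

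The abstract's study design paragraph lists the data to be gathered: "Clinical characteristics, medications, procedure duration, heparin dosage, and post procedure anticoagulation will be collected". On timing, section 4.2 says "Data collection will occur just prior to, and during the ablation procedure", so some of these values exist before the procedure starts.

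On allocation, section 3.2 says "Patients will be randomized 1:1 to either the Manual Hemostasis Group (Control) or to the Figure of 8 Hemostasis Group". Section 3.3 adds "Randomization will be performed by a random number generator", with odd numbers going to control, and describes no stratification or minimization. It also fixes when the arm becomes known: "When the procedure is to begin, the randomization will be" provided.

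**The concern.** Baseline factors that help to predict how long hemostasis takes leave their share of the variance in the standard error when they are not modelled. The same 100 patients might then give a narrower interval and more power than the planned tests deliver. Allocation is not stratified, so prognostic factors are not balanced by design either.

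This matters most if the effect is closer to the second scenario of section 4.1 than to the first, because 50 per arm then leaves little to spare. A practical risk follows: if an imbalance is noticed later in this unblinded trial and adjustment is added then, the choice of covariates would look data-driven.

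**Working it through.** **Inputs.** Section 4.1 gives control 30 ± 15 min and study 15 ± 5 min (main scenario), and study mean 20 with SD 16 (second scenario). It plans 50 per arm and 90% power. Section 4.2 sets the significance level at 0.05. Assumptions: a two-sided test, because sidedness is not stated; control SD 15 carried into the second scenario; R² between 0 and 30%, because the documents give no figure.

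**The plan's own sample sizes.** n per arm = (z₁₋α/₂ + z₀.₉₀)² (s₁² + s₂²)/Δ², with (1.960 + 1.282)² = 10.51.
- Main scenario: 10.51 × (225 + 25)/15² = 11.7, so 12 two-sided (10 one-sided). The stated 10 is close.
- Second scenario: 10.51 × (225 + 256)/10² = 50.5, so 51 two-sided (42 one-sided). The stated 33 does not follow from these inputs. That is a separate matter, but it means that 50 per arm sits at about 90% power in this scenario, not well above it.

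**Power with and without adjustment.** With k covariate terms:
- SE = √[(s₁² + s₂²)/50 × (1 − R²) × F]
- F = 1 + k/(97 − k), the usual average cost of estimating k coefficients in 100 patients (F = 1 when k = 0)
- df = 98 − k, and power comes from the noncentral t distribution with noncentrality Δ/SE.

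Second scenario, Δ = 10:
- Unadjusted: SE = √(481/50) = 3.10, noncentrality 3.22, df 98, power 89.1%, 95% CI half-width 6.2 min.
- Five terms: F = 1 + 5/92 = 1.054, df 93.
- Three terms: F = 1 + 3/94 = 1.032, df 95.

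| R² | Power, cost ignored | Power, 5 terms | CI half-width, 5 terms (min) | Power, 3 terms |
|---|---|---|---|---|
| 0 | 89.1% | 87.4% | 6.3 | 88.1% |
| 5% | 90.6% | 89.0% | 6.2 | 89.7% |
| 10% | 92.0% | 90.6% | 6.0 | 91.2% |
| 20% | 94.6% | 93.5% | 5.7 | 94.0% |
| 30% | 96.8% | 96.0% | 5.3 | 96.4% |

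Break-even is at R² of about 5% with five terms and about 3% with three. The equivalent gain in sample size with five terms is 1/[(1 − R²)F] − 1, which is 5.4%, 18.6% and 35.5% at R² of 10, 20 and 30%.

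**Main scenario, Δ = 15.** SE = √(250/50) = 2.24 and noncentrality 6.71 unadjusted. With five useless terms they are 2.30 and 6.53. Power exceeds 99.99% in both cases.

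**Chance imbalance.** With 50 per arm, the standardized difference in any one covariate has SD √(2/50) = 0.20, so it exceeds 0.2 in absolute value with probability 32%. For R² of 10 to 30% and SD 15.5 (√240.5), a 0.2 SD imbalance moves the estimate by √R² × 15.5 × 0.2 = 1.0 to 1.7 min. The unadjusted standard error of 3.10 min already includes this variation.

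**Validity check.** In simulation (50 per arm, 6,000 runs per setting, one covariate, R² of 0, 10 and 30%), type I error was 4.6 to 5.3% for the t test and 4.7 to 5.1% for the adjusted model.

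**The case against.** A reader might infer that the unadjusted comparison is biased, or that chance imbalance goes uncorrected. The documents do not support this. Allocation is random, the unpaired t test is unbiased over that randomization and keeps its type I error, and its standard error already allows for imbalance.

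A reader might also take the gain as free, which is the cost-ignored column in the table. It is not: covariates that explain nothing lower power.

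Three further objections stand:
- Nothing in the documents links anticoagulant, age, sex or weight to either time. Much of what they describe is procedural: ACT checks and protamine before manual sheath removal, and staff pressure against a physician's suture. Baseline R² could be small.
- Section 4.1 gives one set of figures for an unspecified time. The calculation cannot be claimed for both primary outcomes.
- Neither clinical characteristics nor medications is itemized, so whether age, sex and body weight are recorded is an assumption.

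These objections limit the size of the point and the confidence in it. They do not remove it, because baseline data are to be collected and no adjusted analysis is planned.

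**Conclusion.** The point holds as an inexpensive improvement in efficiency. The planned test is valid. In the second scenario, a five-covariate model changes power from 89.1% to between 87.4% (R² = 0) and 96.0% (R² = 30%), and it helps only above an R² of about 5%. In the main scenario there is nothing to gain in power.

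The result rests on an assumed R², a two-sided 5% test, control SD 15 in the second scenario, and all 50 per arm being evaluable. It describes the single time in section 4.1; the documents give no separate figures for the other primary time. Confidence that no adjustment is planned is high. Confidence in the size of the gain is low.

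**What to change.** In section 4.2, before any comparison by arm, prespecify for each primary time a linear model with arm plus two or three pre-randomization covariates already on the case forms. Candidates are the oral anticoagulant in use at the procedure (coding fixed in advance), age and, if recorded, body weight. A multi-category anticoagulant uses several terms, so count terms and not variables. Use robust standard errors and report the adjusted difference with a 95% CI beside the unadjusted result. State in advance which of the two carries the test, and how missing covariate values are handled.

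Leave heparin dosage, procedure duration and post-procedure anticoagulation out of the model. Section 3.3 releases the arm as the procedure begins, so these are post-randomization values.

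The cost is one paragraph and a few degrees of freedom out of 98, with no new data if the covariates are already on the forms. If the covariates explain nothing, the power loss in the second scenario is about 1.7 points with five terms (89.1% to 87.4%) and about 1.0 point with three (89.1% to 88.1%).
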